### Stimulation-related complications or other complications

- Worsening of motor impairment and Parkinson's disease symptoms including dyskinesia, rigidity, akinesia or bradykinesia, myoclonus, motor fluctuations, abnormal gait or incoordination, ataxia, tremor, and dysphasia
- Paresis, asthenia, hemiplegia, or hemiparesis
- Dystonia
- Sensory disturbance or impairment including neuropathy, neuralgia, sensory deficit, headache, and hearing and visual disturbance
- Speech or language impairment including, aphasia, dysphagia, dysarthria, and hypophonia

## Clinical Investigational Plan

- Cognitive impairment including attention deficit, confusion, disorientation, abnormal thinking, hallucinations, amnesia, delusions, dementia, inability to act or make decisions, psychic akinesia, long term memory impairment, psychiatric disturbances, depression, irritability or fatigue, mania or hypomania, psychosis, aggression, emotional lability, sleep disturbance, anxiety, apathy, drowsiness, alteration of mentation, postural instability and disequilibrium
- Restless leg syndrome
- Supranuclear gaze palsy
- Hypersexuality or increased libido
- Decreased therapeutic response
- Urinary incontinence or retention
- Diarrhea or constipation
- Cardiac dysfunction (e.g., hypotension, heart rate changes, or syncope)
- Difficulty breathing
- Increased salivation
- Weight gain or loss
- Eye disorder including eye apraxia or blepharospasm
- Nausea or vomiting
- Sweating
- Fever
- Hiccups
- Cough
- Cramps
- Worsening existing medical conditions

### 3.4 RESIDUAL RISKS ASSOCIATED WITH THE DEVICE UNDER INVESTIGATION, AS IDENTIFIED IN THE RISK ANALYSIS REPORT

DBS refers to the electrical stimulation of structures deep within the brain. DBS is considered an effective treatment for Parkinson's disease, tremor and dystonia that is reversible, and adaptable.

The targeted study population consists of subjects who have been implanted with or are being considered for implant of an Infinity DBS system. Standard outcome measures will be used to evaluate Parkinson's disease symptoms.

Effects of the DBS are considered safe, non-destructive and reversible. The frequency and severity of procedural risks and complications related to the implant of the Infinity system are expected to be similar to those that are cited in the current literature.

### 3.5 RISKS ASSOCIATED WITH PARTICIPATION IN THE CLINICAL STUDY

There are no study-related additional risks expected within this study.

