#### 4.5.2 Exclusion Criteria

- 1) Subject is not a surgical candidate;
- 2) In the investigator's opinion, the subject is unable to tolerate multiple programming sessions within a single setting;
- 3) Subject is unable to comply with the follow-up schedule.

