## Clinical Investigational Plan

### 6.0 PROCEDURES

#### 6.1 STUDY FLOW CHART

**Subjects may be enrolled after device implant**

### Clinical Investigational Plan

## 6.2 STUDY VISITS

The clinical study will be conducted in accordance with the CIP. All parties participating in the conduct of the clinical study will be qualified by education, training, or experience to perform their tasks and this training will be documented appropriately.

The clinical study will not commence until St. Jude Medical receives written approval from the EC or IRB and relevant regulatory authorities and all required documents have been collected from the site(s).

Table 1: List of all study specific activities/procedures

Visit Study Activity	Enrollment Baseline	Implant	Initial Programming site standard of care – Omnidirectional (Day 0)***	3 Month 3 months $\pm$ 30 days since Initial Programming – Directional	6 Month 6 months $\pm$ 30 days since Initial Programming	12 Month 12 months $\pm$ 60 days since Initial Programming	24 Month 24 months $\pm$ 90 days since Initial Programming	36 Month 36 months $\pm$ 90 days since Initial Programming
Inclusion/Exclusion Criteria check	X							
Informed Consent Process	X							
Subject Demographics	X							
Parkinson's Disease History	X							
Parkinson's Disease Medication Current	X					X		X
UPDRS Section II and III Off Medication	X							
UPDRS Section II and III On Medication	X							
UPDRS Section II (On Med On Stim)				X	X	X		X
UPDRS Section III (Off Medication / On Stim)				X*		X		X
UPDRS Section III (Off Medication / Off Stim)				X*		X		X
UPDRS Section III (On Med On Stim)				X*	X*	X		X
UPDRS Section III (On Med Off Stim)				X*	X*	X		X
PDQ-39	X			X	X	X		X
Implant Information		X						
Pre- and Post-Operative Image Collected		X						
Initial testing/ programming data/session data			X*					
Subject Preference					X**			
Clinician Preference					X			

Clinical Investigational Plan

Visit Study Activity	Enrollment Baseline	Implant	Initial Programming site standard of care – Omnidirectional (Day 0)**	3 Month 3 months ± 30 days since Initial Programming – Directional	6 Month 6 months ±30 days since Initial Programming	12 Month 12 months ± 60 days since Initial Programming	24 Month 24 months ±90 days since Initial Programming	36 Month 36 months ±90 days since Initial Programming
System Usability Scale (SUS) Subject						X		
System Usability Scale (SUS) Programmer						X		
Device Testing/ Programming data /session data				X*	X	X*		X

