### 6.6 SCHEDULED FOLLOW-UPS

#### Blinded Evaluation

A blinded evaluator will be used in this study to minimize study bias. The blinded evaluator will assess the therapeutic window for each subject at the initial programming, the 3-month visit and at the 12-month visit. The UPDRS part III motor examination for each subject will also be assessed by the blinded evaluator at the 3-month and 6-month visits. This evaluator will not be aware of the subject's programming or device settings. It is recommended that the blinded evaluator assessing the therapeutic window and the UPDRS part III motor examination should be the same person; however, it is not required. In addition, subjects will be unaware of their programmed parameters for the first 6 months.

Subjects are to be instructed not to take medication the night prior to or the morning of the study visit. This is defined as the Off Medication state. Upon taking appropriate medication, subject is considered to be in the On Medication state.

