#### 3-Month Follow-Up Visit (3 months ± 30 days since initial programming or consent date)

The following information will be collected at the 3-month follow-up visit:

- PDQ-39;
- UPDRS part II ADLs On Medication / On Stimulation;
- UPDRS part III motor examination Off Medication/Off and On Stimulation assessed by a blinded evaluator;
- UPDRS part III motor examination On Medication/ Off and On Stimulation assessed by a blinded evaluator;
- Omnidirectional testing – Off Medication (See Evaluation of Programming)
- Detailed directional lead testing as tolerated by the subject – Off Medication (see Evaluation of Programming); sites are to program each lead to the optimal directional segment;
- Programming parameters; device session data;
- Unscheduled visits (if applicable);

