### 6-Month Follow-Up Visit (6 months ± 30 days since initial programming or consent date)

The following information will be collected at the 6-month follow-up visit:

- PDQ-39;
- UPDRS part II ADLs On Medication / On Stimulation;
- UPDRS part III motor examination On Medication/ Off and On Stimulation assessed by a blinded evaluator;
- Programming parameters; device session data;
- Subject and clinician preference;
- Unscheduled visits (if applicable);
- AE, system revision, and/or protocol deviation (if applicable).

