### Evaluation of Programming/Device Testing:

Device testing is to be completed with the subject in the Off Medication state.

Subjects are to be instructed not to take their medication the night prior to or the morning of the study visit; or depending on the type of levodopa medication the subject is taking (i.e.; extended release or long acting) the investigator can use clinical judgement to determine an adequate length of time that the subject should be off medication prior to the testing.

**In order to minimize programming bias, each site will have a designated programmer and a designated blinded evaluator during the omnidirectional and directional device testing. The blinded evaluator will be unaware of the specific program changes made to the device parameters during each testing.**

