**SAE Reporting**

The investigator should report all SAEs to the Sponsor as soon as possible but no later than outlined below.

Clinical Site	Reporting timelines
All Sites	SAEs must be reported to the Sponsor no later than 3 calendar days from the day the site personnel became aware of the event or as per the investigative site’s local requirements, if the requirement is more stringent than those outlined.

The date the site staff became aware the event met the criteria of an SAE must be recorded in the source document. The Investigator will further report the SAE to the local IRB/EC according to the institution’s IRB/EC reporting requirements.

Reportable events to sponsor are considered:

- 1) All Serious Adverse Events;
- 2) All device related Adverse Events (whether or not the event is considered serious).

Procedure related AEs as noted in Section 3.3 that are not identified as Serious Adverse Events should only be reported if they become severe, become reportable as an SAE, or if they continue for greater than 30 days after the surgery date. The following commonly reported procedure related AEs should only be reported as AEs if they continue for longer than 30 days postoperatively:

- Headache
- Persistent pain at surgery site or IPG site
- Post-operative pain, stress, or discomfort

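### The plan says participation adds no risk, yet it requires off-medication and off-stimulation testing, and a non-serious, non-severe event caused only by withheld medication fits no reportable category

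*Combined protocol and SAP*

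**What the plan says.** **Risk.** The sentence "There are no study-related additional risks expected within this study" is the whole of section 3.5 (risks of participation), section 3.7 (mitigation) and section 3.8 (risk-to-benefit rationale). Section 4.2 adds that participants face only the risks of having a DBS system implanted.

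**Procedures.** The schedule in section 6.2 is headed "Table 1: List of all study specific activities/procedures". It includes UPDRS part III exams off medication, off stimulation, and both. Section 6.6 repeats them by visit, for example at month 3: "UPDRS part III motor examination Off Medication/Off and On Stimulation assessed by a blinded evaluator". Device testing is done off medication, and amplitude is raised in each configuration until a sustained side effect is seen. Section 4.5.2 excludes a subject if, in the investigator's opinion, "the subject is unable to tolerate multiple programming sessions within a single setting".

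**Reporting.** Section 8.2 (SAE Reporting) introduces its list with "Reportable events to sponsor are considered" and names two groups: all serious adverse events, and all device-related adverse events, serious or not. Non-serious procedure-related events noted in section 3.3 are reported only if they become severe, become serious, or last more than 30 days after surgery. Section 4.2 gives a similarly limited recording scope.

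**Withholding.** Under Blinded Evaluation, within the scheduled follow-ups of section 6.6: "Subjects are to be instructed not to take medication the night prior to or the morning of the study visit". Under Evaluation of Programming/Device Testing: "Subjects are to be instructed not to take their medication the night prior to or the morning of the study visit", followed by an allowance for investigator judgement by type of levodopa. The month 6 visit lists only "UPDRS part III motor examination On Medication/ Off and On Stimulation assessed by a blinded evaluator".

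**The concern.** The risk sections and the visit schedule do not describe the same study. The schedule requires periods without medication, without stimulation, or without either. The risk sections do not mention them, and section 3.7 gives no mitigation even though the plan contains some elsewhere.

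Two practical consequences follow. First, the adverse event scope is built around the device and the implant surgery. An event that arises only because a subject went without medication for a study visit has no obvious place in it. If such an event is neither serious nor severe, a site that follows the plan need not record it, so the data could not show whether this part of the no-added-risk statement is right.

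Second, sites can read the withholding instruction differently at month 6. That affects what subjects are asked to do. It also touches secondary endpoint 2, which compares part III at months 3 and 6: On Medication is the only medication state examined at both visits, and what precedes that exam at month 6 would depend on which paragraph a site follows.

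**Working it through.** No sample size, power or error rate is involved. The check is a count from Table 1 and a reading of the reporting categories.

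**Step 1. Count the exams and visits** (Table 1, section 6.2, and visit lists, section 6.6).

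| Visit | Off-medication device testing | Part III Off Med/On Stim | Part III Off Med/Off Stim | Part III On Med/Off Stim |
|---|---|---|---|---|
| Initial programming | 1 | 0 | 0 | 0 |
| Month 3 | 1 | 1 | 1 | 1 |
| Month 6 | 0 | 0 | 0 | 1 |
| Month 12 | 1 | 1 | 1 | 1 |
| Month 36 (optional) | 1 | 1 | 1 | 1 |

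To month 12:
- visits with off-medication testing: 1 + 1 + 1 = 3
- stimulation-off part III exams: 2 + 1 + 2 = 5
- medication-off part III exams: 2 + 2 = 4
- exams with either or both withheld: 4 + 5 − 2 (both withheld) = 7

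Adding month 36, which sections 4.2 and 4.6.2 make optional under a separate consent addendum:
- visits with off-medication testing: 3 + 1 = 4
- stimulation-off exams: 5 + 2 = 7
- medication-off exams: 4 + 2 = 6
- either or both withheld: 6 + 7 − 3 = 10

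These are visits, not days. The 3-month testing instructions, which are repeated at months 12 and 36, allow testing to be spread over several days of one week.

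**Step 2. Classify a non-serious, non-severe event caused only by withheld medication.**
- Serious adverse event: no, by assumption.
- Device-related: no. Section 8.1.3 requires a relation to use of the device, including its operation, and here the cause is the missing medication.
- Procedure-related: no, on the best reading. Section 8.2 ties this group to the events noted in section 3.3 and counts the 30 days from surgery, so the procedure is the implant. The severity trigger is not met, by assumption.
- Section 4.2: no. It lists serious events, serious procedure-related events, procedure-related events beyond 30 days, and device-related events.

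The event meets the broad adverse event definition in section 8.1.1, but section 6.3 refers sites to the protocol's reporting guidelines, and section 8.2 sets what is reported.

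**Step 3. Compare the withholding texts.** Blinded Evaluation refers to the study visit, without naming which, and to medication in general. The device-testing text repeats the instruction in the context of testing and allows judgement by medication type. Month 6 has no device testing off medication and no off-medication exam. If the first text is applied at month 6, withholding visits rise from 3 to 4 by month 12, and from 4 to 5 by month 36. If the other two are followed, they do not.

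**The case against.** The strongest reply is that the plan captures most of what matters. All serious events are reportable whatever their cause. Device-related events are reportable at any severity, and harm from switching stimulation off or raising amplitude can be classed there. A severe event of a kind listed in section 3.3, such as dystonia, might be reported through the severity trigger. The term procedure is undefined, section 8.1.1 refers broadly to the procedures involved, and the 24-month visit text speaks of all adverse events being reported. The descriptive safety endpoint is device-related events, so a limited scope fits the stated aim.

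Much of this stands. A reader might infer that the study cannot detect harm from its own procedures; the documents do not support that. The gap is confined to non-serious, non-severe events due solely to withheld medication. The wider phrases do not close it: the 24-month text covers only the optional long-term follow-up, and section 8.2 remains the operative list.

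It can also be said that the title of Table 1 proves little, since the table includes routine items; that baseline off-medication scores may come from existing records; and that initial programming follows site practice. This is fair. But the plan nowhere calls the later off-state exams standard of care, and subjects already implanted are tested off medication on the consent date because they enrolled.

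Mitigation does exist: the tolerance exclusion, testing as tolerated, suggested rest periods, fatigue rating and judgement on time off medication. The fault is that section 3.7 mentions none of it. Section 3.5 also speaks of risks expected, which is softer than section 4.2.

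A reader might further infer that subjects consent on the no-risk statement. The consent form was not available for review, so this cannot be judged. Section 3.6 deals with diathermy and MRI and does not carry the sentence.

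**Conclusion.** The point holds in a limited form. Sections 3.5, 3.7, 3.8 and 4.2 do not match Table 1 and section 6.6, which require 3 visits with off-medication testing and 5 stimulation-off part III exams by month 12, or 4 and 7 for subjects who continue to month 36. One class of event, non-serious, non-severe and caused only by withheld medication, fits no category in section 4.2 or 8.2. This rests on reading procedure-related as the implant procedure, which the link to section 3.3 and the surgery date supports but no definition settles.

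The month 6 withholding instruction is ambiguous on the text. The number of subjects affected cannot be derived: enrolment is capped at 350, which is only an upper bound before attrition and depends on which paragraph each site follows. The documents give no rate for the unreported events either, so no size can be put on the loss.

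The changes to reporting scope and visit instructions matter most, because they alter what is recorded and what sites do. Rewording the risk sections alone would be weaker.

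**What to change.** 1. In sections 4.2 and 8.2, add a reportable category for adverse events judged related to study-specific assessments, including medication withholding. Reconcile the broader wording in the 24-month visit text with section 8.2.
2. Reconcile three parts of section 6.6 (Blinded Evaluation, the 6-month visit, and Evaluation of Programming/Device Testing) so that the withholding instruction agrees across visits. Which rule applies is a clinical decision for the sponsor and investigators; none is proposed here.
3. Correct sections 3.5, 3.7, 3.8 and the corresponding sentence in 4.2 so that they describe the study-specific procedures and the mitigations already in sections 4.5.2 and 6.6. Check that the consent form agrees.

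The cost is protocol wording, one relatedness option on the adverse event form, and a modest number of additional adverse event entries.

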### 3.6 POSSIBLE INTERACTIONS WITH CONCOMITANT MEDICAL TREATMENTS AND/OR CONCURRENT MEDICAL INTERVENTIONS

Diathermy therapy is contraindicated for subjects who have been implanted with the Infinity system. Do not use short-wave diathermy, microwave diathermy, or therapeutic ultrasound diathermy (all now referred to as diathermy) on subjects implanted with a neurostimulation system. Energy from diathermy can be transferred through the implanted system and can cause tissue damage at the location of the implanted electrodes, resulting in a severe injury or death. Diathermy is further prohibited because it may also damage the neurostimulation system components. This damage could result in loss of therapy, requiring additional surgery for system replacement. Injury or damage can occur during

## Clinical Investigational Plan

diathermy treatment whether the neurostimulation system is turned on or off. All subjects are advised to inform their healthcare professional that they should not be exposed to diathermy treatment.

Magnetic resonance imaging (MRI) may be contraindicated for subjects implanted with the Infinity system. If the Infinity system has MRI Conditional labelling, MRI may be performed with imaging settings described in Abbott's DBS MRI Procedures Manual. If the Infinity system does not have MRI Conditional labelling, do not use a full body radiofrequency (RF) coil or other extremity coils on subjects implanted with a neurostimulation system. Because energy from MRI can be transferred through the implanted system, the potential for heat generation at the location of the electrodes exists. This isolated temperature rise may cause tissue damage at the location of the implanted electrodes, possibly resulting in severe injury or death. Injury can occur during MRI treatment whether the neurostimulation system is turned on or off. Patients with a neuromodulation system that does not have MRI Conditional labelling are advised to inform their healthcare professional that they should not be exposed to MRI.

Please refer to the Infinity IPG clinician manual/instructions for use regarding warnings and precautions.

### 3.7 STEPS THAT WILL BE TAKEN TO CONTROL OR MITIGATE THE RISKS

There are no study-related additional risks expected within this study.

### 3.8 RISK-TO-BENEFIT RATIONALE

There are no study-related additional risks expected within this study.

### 3.9 DESCRIPTION OF HISTORY OF MODIFICATIONS OR RECALL IN RELATION TO SAFETY AND CLINICAL PERFORMANCE FOR DEVICE UNDER INVESTIGATION

This is a newly approved device and no device modifications have been reported to date. No device recalls have been issued concerning this product.

## 4.0 STUDY DESIGN

### 4.1 PURPOSE

The purpose of this post market study is to characterize the clinical performance of the Infinity DBS system including IPG, leads, extensions and related system components.

The PMCF requirement for this study will be to demonstrate superiority of directional stimulation compared to omnidirectional stimulation, as measured by therapeutic window. The primary endpoint will be evaluated for the first 66 subjects who complete the 12-month follow-up visit and have evaluable primary endpoint at the 3-month follow-up visit.

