### Clinical Investigational Plan

	
Total amount of time required for each study visit and programming. Long-term outcomes evaluated by change compared to baseline in UPDRS part III motor examination, UPDRS part II ADLs and PDQ-39, at the 36-month follow-up visit.

Design	
This study is designed as a prospective, blinded-subject, blinded-evaluator, observational, multi-center 36 month post market clinical follow up study. The total duration of this study is expected to be 60 months. The clinical study will be conducted at up to 60 centers in the European Union, United States, Latin America, and Australia. Up to 350 subjects will be enrolled. The primary endpoint analysis will be performed when 66 subjects have completed 12 months of follow-up and have evaluable primary endpoint at the 3-month follow-up visit. Interim annual progress reports will be reported to comply with Post-Market Clinical Follow-up (PMCF) requirements.
 
Baseline data can be collected from the subject’s medical records to compare to follow-up visits. Data will be collected 3, 6, 12, 24 and 36 months after initial programming for comparison to baseline.
 
A subset of subjects enrolled in this study will be used to meet the PMCF requirement for CE mark. Once this subset of subjects is enrolled and followed for 12 months and have evaluable primary endpoint at the 3-month follow-up visit, a report will be submitted indicating completion of this requirement.

Devices Used	
The following devices will be used in the study:
 
 
Infinity DBS System
 
Infinity DBS system including Implantable Pulse Generator (IPG), the 4 and 8 channel leads and accessories
 
Infinity Clinician Programmer App and Patient Controller App
 

Study Population	
Subjects who have a diagnosis matching the approved indication and are being considered for a DBS implant or who have been implanted with an Infinity system comprise the target population for this study. Subjects who meet all of the inclusion criteria and none of the exclusion criteria, and who have signed a statement of informed consent approved by an Ethics Committee (EC) or Institutional Review Board (IRB), will be enrolled in the study.
 
The PMCF requirement will be complete when 66 subjects have been followed for 12 months and have evaluable primary endpoint at the 3-month follow-up visit.

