## Clinical Investigational Plan

and have evaluable primary endpoint data at the 3-month follow-up visit, a report will be submitted indicating completion of this requirement. The primary endpoint analysis will be performed when 66 subjects have completed 12 months of follow-up and have evaluable primary endpoint data at the 3-month follow-up visit.

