### 6.12 CRITERIA AND PROCEDURES FOR SUBJECT WITHDRAWAL OR DISCONTINUATION

Each subject should remain in the study until completion of the required follow-up period; however, a subject's participation in the study may be discontinued at any time. Should this occur, the reason for discontinuation must be documented in the withdrawal form.

Subjects must be informed about their right to withdraw from the study at any time and for any reason without sanction, penalty or loss of benefits to which the subject is otherwise entitled and withdrawal from the study will not jeopardize their future medical care or relationship with the investigator. Subjects will be asked to specify the reason for the termination, but have the right not to answer.

The investigator may decide to withdraw a subject from the study at any time with reasonable rationale. The subject's future care will not be influenced by a decision, voluntary or otherwise, to withdraw from the study. All reasonable efforts should be made to retain the subject in the clinical study until completion of the study.

Reasons for subject's withdrawal include, but are not limited to:

- Subject refuses to continue participating in the study
- Subject does not meet the inclusion/exclusion criteria and does not require additional follow-up for safety reasons.
- Subject undergoes a system revision or system explant
- Subject is deceased (cause must be documented)
- Subject's non-compliance
- Subject's participation is terminated by the PI or investigator, although the subject consented, since participation is no longer medically appropriate
- Subject is lost to follow-up: Subject does not adhere to the scheduled follow-up visits but has not explicitly requested to be withdrawn from the clinical study. (This does not apply to missed visits).

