### 12.0 STATISTICAL CONSIDERATIONS

#### 12.1 STATISTICAL DESIGN, HYPOTHESES, METHOD AND ANALYTICAL PROCEDURES

A subset of subjects enrolled in this study will be used to meet the Post Market Clinical Follow-Up (PMCF) requirement for CE mark. Once this subset of subjects is enrolled and followed for 12 months and have evaluable endpoint data at the 3-month follow-up visit, a report pertaining to primary endpoint and secondary endpoints analyses will be submitted indicating completion of this requirement.

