#### Analysis

The primary endpoint will be tested at the 5% significance level. The analysis population includes subjects who have evaluable therapeutic window using omnidirectional and directional stimulation. The analysis will be carried out by calculating the 95% lower confidence bound (LCB) on the success rate using the Clopper-Pearson exact method. The null hypothesis will be rejected if the 95% lower confidence bound (LCB) for  $p$  is greater than 0.60.

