### 12.8 PROCEDURES THAT TAKE INTO ACCOUNT ALL THE DATA

Analyses will be performed in subjects who have evaluable therapeutic windows for both omnidirectional and directional stimulation for the primary endpoint and the first secondary endpoint. The analysis will be performed in subjects who have 3- and 6-month UPDRS part III motor examination

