### 12.12 TIMING FOR ANALYSES

The dataset will be frozen for analysis when 66 subjects have completed the 12-month visit and have evaluable primary endpoint at the 3-month follow-up visit to support the minimum requirements to meet the Post Market Clinical Follow-Up (PMCF) requirement for CE mark.

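### Section 4.1 tests the 3-month primary endpoint only in subjects who also complete month 12, and 12.1.1 and 12.8 do not say whether they apply within that subset

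*Combined protocol and SAP*

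**What the plan says.** Section 4.1 names the set for the primary endpoint: it is "evaluated for the first 66 subjects who complete the 12-month follow-up visit and have evaluable primary endpoint at the 3-month follow-up visit". That makes three conditions: an evaluable month-3 result, a completed month-12 visit, and a place among the first 66.

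The statistical sections state only the first condition. Section 12.1.1: "The analysis population includes subjects who have evaluable therapeutic window using omnidirectional and directional stimulation". Section 12.8: "Analyses will be performed in subjects who have evaluable therapeutic windows for both omnidirectional and directional stimulation for the primary endpoint". Neither mentions month 12 or the number 66, and neither refers back to 4.1.

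Other sections use the same 66 for timing. Section 4.2.1: "The primary endpoint analysis will be performed when 66 subjects have completed 12 months of follow-up". Section 12.12: "The dataset will be frozen for analysis when 66 subjects have completed the 12-month visit". Both add the condition of an evaluable month-3 endpoint. The synopsis and the opening of 12.1 link the PMCF report to a subset. The synopsis says "A subset of subjects enrolled in this study will be used to meet the PMCF requirement for CE mark", and 12.1 places the report on the primary and secondary analyses "Once this subset of subjects is enrolled and followed for 12 months and have evaluable endpoint data at the 3-month follow-up visit".

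Section 12.10 states no intention to exclude information from the hypothesis test. Section 12.9 rules out imputation. Among the reasons for withdrawal in 6.12 is "Subject undergoes a system revision or system explant".

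**The concern.** The primary endpoint is complete at month 3. Under 4.1, whether a subject counts is decided up to nine months later by events that cannot alter that result. Someone with both windows measured at month 3 drops out of the test if they die, withdraw or miss the month-12 visit, and the next completer takes the place. Section 6.12 keeps a subject who misses a visit in the study, so a single missed month-12 visit would exclude from the test a subject who is still being followed.

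This is selection on post-endpoint status, and it sits awkwardly with 12.10. It matters if leaving is related to the month-3 result. Leavers might be successes less often, because a poor response may lead to withdrawal. They might be successes more often, because the background in 2.0 argues that directional stimulation helps most with misplaced or migrated leads, which are also candidates for revision. The test has a strict cutoff at 60%, so the set that carries it should be stated once and should not depend on later events.

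**Working it through.** **Inputs from the plan.** Null rate 0.60, 5% level, exact Clopper-Pearson 95% lower bound that must exceed 0.60 (12.1.1); planning success rate 0.75 (12.2); n = 66 (4.1, 12.12).

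**Inputs assumed.** The loss f between months 3 and 12, and the success rate pd among leavers. Neither is visible, since part of 12.2 is redacted.

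**1. The rule at n = 66.** For x successes in n, the lower bound is the 0.05 quantile of Beta(x, n − x + 1).
- 46/66 gives 0.591 (fail) and 47/66 gives 0.607 (pass), so at least 47 successes are needed.
- P(X ≥ 47 | n = 66, p = 0.60) = 3.95%.
- P(X ≥ 47 | n = 66, p = 0.75) = 80.5%.

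The size of 66 is therefore reasonable for this test. The target power is redacted, so the plan's own calculation cannot be fully reproduced. The number 66 is not in dispute.

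**2. Effect of selection on the false-pass probability.** Let the true rate among all subjects evaluable at month 3 be 0.60. The rate among completers is then pc = (0.60 − f × pd) / (1 − f), and the false-pass probability is P(X ≥ 47 | n = 66, pc).

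| Assumed loss f | Leaver success pd | pc | False pass |
|---|---|---|---|
| 5% | 40% | (0.60 − 0.020)/0.95 = 0.611 | 5.7% |
| 5% | 50% | (0.60 − 0.025)/0.95 = 0.605 | 4.7% |
| 5% | 80% | (0.60 − 0.040)/0.95 = 0.589 | 2.7% |
| 10% | 40% | (0.60 − 0.040)/0.90 = 0.622 | 8.2% |
| 10% | 50% | (0.60 − 0.050)/0.90 = 0.611 | 5.8% |
| 10% | 80% | (0.60 − 0.080)/0.90 = 0.578 | 1.7% |
| any | 60% (loss unrelated) | 0.600 | 3.95% |

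The exact test runs below its nominal level (3.95% against 5%), and this slack absorbs some of the selection. At 5% loss the false-pass probability exceeds 5% only if leaver success is below about 47%.

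**3. When the verdict can change.** Take 4 leavers with valid month-3 results, which is about 5% loss (66/0.95 = 69.5, so 70 subjects). At n = 70 the bound is 0.597 for 49 successes (fail) and 0.612 for 50 (pass).
- With 45 or fewer successes in 66, the most that 70 can reach is 49: fail in both sets.
- With 46 in 66 (fail), 4 successes in 4 leavers give 50/70: pass.
- With 47, 48 or 49 in 66 (pass), the larger set fails if the leavers add fewer than 3, fewer than 2, or none.
- With 50 or more in 66: pass in both sets.

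The choice of set can therefore reverse the result in either direction, but only for 46 to 49 successes in 66.

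**The case against.** The strongest reply is that the set is already fixed. Section 4.1 names it, 12.1 opens with the same subset and ties the report on the primary and secondary analyses to it, and 12.1.1 and 12.8 then only define what evaluable means. On that view the sections intersect and all that is missing is a cross-reference. Most of this stands. A reader might infer that 4.1 and the statistical sections flatly contradict each other. The documents do not support that: neither 12.1.1 nor 12.8 claims all evaluable subjects or overrides 4.1. Part of 12.2 is redacted, so one can say only that no visible text settles the question. But the intersection reading does not remove the problem. It confirms that a month-3 result can be discarded because of later events.

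Second, the link between loss and outcome is not shown. Revision or explant is a listed withdrawal reason, yet the visit schedule also records system revisions at follow-up visits, so a revision need not mean loss before month 12. No section connects leaving with the month-3 window. This stands too, and it is why the direction of bias is left open.

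Third, 12.8 and 12.9 require subject accountability and reasons for excluded data, so leavers would be visible in the report. That helps a reader, but it does not say which set carries the test.

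**Conclusion.** The concern holds as a modest design point that should be fixed. Followed as written, 4.1 selects the primary set on month-12 status, and the visible text never states how 12.1.1 and 12.8 relate to that set.

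Under assumed loss of 5% to 10% and leaver success of 40% to 50%, the false-pass probability is 4.7% to 8.2%, against 3.95% without selection. If leavers do better than completers, it falls below 3.95%. If loss is unrelated to the month-3 result, there is no bias.

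Two stronger inferences should be resisted. One is that the completer set favours the device: nothing in the documents fixes the direction. The other is that the error is large. A false-pass probability of 15.4% can be computed, but only with 10% loss and 20% success among leavers, against 64.4% among completers. Comparing the 66 with a set of 132 subjects gives disagreement of up to 34.3% at a true rate of 70%. That needs 66 assumed extra subjects and mostly reflects the power of a larger sample. If loss is unrelated, swapping a few subjects at fixed n also produces some disagreement, but that is sampling noise, not bias.

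**What to change.** Keep 66 month-12 completers with an evaluable month-3 endpoint as the trigger for the data freeze and the PMCF report (synopsis, 4.2.1, 12.12). In 4.1, 12.1.1 and 12.8, define one primary set without reference to month-12 status: for example, the first 66 consecutive subjects, by date of the 3-month visit, with both windows evaluable. At least 66 such subjects must exist at the freeze, so n stays at 66. That set also leaves out some evaluable subjects, so report two sensitivity analyses: the 66 completers, and everyone evaluable at month 3 by the freeze.

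Timing matters. Section 12.4 plans an unblinded interim analysis as more subjects reach month 3, so the set must be fixed before any unblinded 3-month data are seen. If such data have already been seen, keep the completer set as primary, state in 12.1.1 and 12.8 that they apply within it, and report the month-3-evaluable result beside it.

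The cost is wording in these sections and two extra tabulations of data already collected. The reported success rate may shift slightly in either direction, and the completer result becomes a sensitivity analysis.
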